10.3.5. Pharmacokinetic/Pharmacodynamic Analyses

The PK of mirikizumab will be characterized using graphical evaluations and mixed-effect (population PK) modeling approaches. Various structural and error models will be evaluated

during development of the mixed-effect model. Intrinsic factors (such as, age, body weight, gender, ADAs, etc.) and extrinsic factors (such as, co-medications) will be investigated to assess their influence on model parameters. Model evaluation will include a visual predictive check. Estimates of PK model parameters and covariate effects and the corresponding 90% CIs will be reported.

Analyses of exposure-response relationships will be conducted using both exploratory graphical approaches and model based approaches. Exploratory graphical analysis approaches may consist of graphs showing the percentage of patients who achieve clinical response, clinical remission, and endoscopic remission at different percentiles (for example, quartiles) of exposure of mirikizumab at Week 40. Measures of exposure may include population PK estimated average concentrations (C_{avg}) between Week 0 and Week 40, or estimated or observed trough concentrations at Week 40. Model based analyses will utilize population exposure-response logistic regression models, where maximum effect (E_{max}) or other model structures may be used to relate exposure to the probability of achieving clinical response, clinical remission, and endoscopic remission. These models may be used to evaluate patient factors that may impact the relationship between exposure and the probability of achieving the endpoint. Longitudinal exposure-response models for SF and RB subscores may be developed, which relate the time course and magnitude of mirikizumab exposure to the time course of these subscores.

Additional analyses may be conducted if they are deemed appropriate. Data from this study may be combined with other study data, if appropriate. Further details on PK and PK/PD analyses will be provided in the PK/PD analysis plan.

10.3.6. Evaluation of Immunogenicity

The frequency and percentage of patients with preexisting (baseline) ADA, ADA at any time post baseline, and with treatment-emergent (TE)-ADA to mirikizumab will be tabulated. If no ADAs are detected at baseline, TE-ADA are defined as those with a titer 2-fold (1 dilution) greater than the minimum required dilution of the assay. For samples with ADA detected at baseline, TE-ADA are defined as those with a 4-fold (2 dilutions) increase in titer compared to baseline. For patients who have TE-ADA, the distribution of maximum titers will be described. The frequency of neutralizing antibodies will also be tabulated.

The relationship between the presence of antibodies and the PK parameters and PD response, including safety and efficacy to mirikizumab, may be assessed.

10.3.7. Other Analyses

10.3.7.1. Subgroup Analyses

Subgroup analyses will be conducted for the primary endpoint and selected major secondary endpoints. Subgroups to be evaluated will include sex, age category, body weight, race, geographic region, baseline disease severity, duration of disease, previous biologic-failed status (yes or no), corticosteroid use (yes or no), UC concomitant therapy use (corticosteroid, immunomodulators), induction remission status (yes or no) for endpoints among induction responders. The treatment-by-subgroup interaction will be tested at the significance level

of 0.10. If any treatment group within the subgroup is less than 10% of the total mITT population for the main cohort, only summaries of the efficacy data will be provided (that is, no inferential testing will be done).

Detailed subgroup analysis will be defined in the SAP.

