A prespecified multiple testing scheme based on graphical approach (Bretz et al. 2009, 2011) will be used to test the primary and major secondary hypotheses at overall family wise type 1 error rate (FWER) of 0.05. The graphical approach is a closed testing procedure, hence, it strongly controls the FWER across all endpoints (Alosh et al. 2014). Details of the specific graphical testing scheme (including testing order, interrelationships, type I error allocation for

the major secondary endpoints, and the associated propagation) will be prespecified in the statistical analysis plans (SAPs) prior to first unblinding of efficacy.

The Fisher exact test will be used to perform the between-treatment group comparisons for adverse events (AEs), discontinuations, and other categorical safety data. The change from baseline in continuous vital signs, physical characteristics, and other continuous safety variables, including laboratory variables, will be summarized by visit and treatment. Shift tables for categorical safety analyses (for example, “high” or “low” laboratory results) will also be produced.

No multiplicity control approach will be used for testing of other secondary endpoints.

2. Schedule of Activities

Table AMBG.2.1. Schedule of Activities – Responders from Induction Study

Procedure	Randomized Maintenance Period												Post-treatment Follow-up		Notes		
	Visit	V1	V2	V3	V4	V5	V6	V7	V8	V9	V10	V11	N/A	V997		801	802
Week	0	4	8	12	16	20	24	28	32	36	40 LV	ETV	UV	LV or ETV +4	LV or EIV +12/16 ^b		
Day and/or Visit Interval Tolerance	1 ^a	29 +/-7	57 +/-7	85 +/-7	113 +/-7	141 +/-7	169 +/-7	197 +/-7	225 +/-7	253 +/-7	281 +/-7	N/A	N/A	+/-10	+/-10		
Informed consent	X																Patients may consent between the start of V5 of Study AMAN and before any procedures at V1/Week 0 are performed.
Inclusion and exclusion criteria	X																Can begin at Week 12 of induction and continue until dosing is initiated in Study AMBG.
Concomitant medication	X	X	X	X	X	X	X	X	X	X	X	X	X	X	X	X	
Review AEs	X	X	X	X	X	X	X	X	X	X	X	X	X	X	X	X	
Tobacco/nicotine use	X ^c			X			X				X	X					
IP Administration																	
IWRS/Randomization	X																
IP SC administration	X	X	X	X	X	X	X	X	X	X							

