
 To evaluate the efficacy of mirikizumab compared to placebo in achieving clinical remission at Week 40 among patients induced into clinical response with mirikizumab, in the subgroup of patients in whom biologic agents have failed or caused intolerance. 	
 Clinical remission at Week 40 in the subgroup of patients in whom biologic agents have failed or caused intolerance. Clinical remission is defined as: 
 SF subscore = 0 or SF = 1 with a ≥ 1-point decrease from induction baseline, and RB subscore = 0, and ES = 0 or 1 (excluding friability)

 To evaluate the efficacy of mirikizumab compared to placebo in achieving endoscopic remission at Week 40 among patients induced into clinical response with mirikizumab, in the subgroup of patients in whom biologic agents have failed or caused intolerance. 	
 Endoscopic remission at Week 40 in the subgroup of patients in whom biologic agents have failed or caused intolerance. Endoscopic remission is defined as: ES = 0 or 1 (excluding friability)

 To evaluate the efficacy of mirikizumab as compared to placebo in maintaining clinical remission at Week 40 (Week 52 of continuous therapy) among patients induced into clinical remission with mirikizumab, in the subgroup of patients in whom biologic agents have failed or caused intolerance 	
 The proportion of patients who were in clinical remission at Week 40 among patients in clinical remission at Week 12 in Study AMAN (i.e. durable clinical remission) in whom biologic agents have failed or caused intolerance. Clinical remission is defined as: 
 SF subscore = 0 or SF = 1 with a ≥ 1-point decrease from induction baseline, and RB subscore = 0, and ES = 0 or 1 (excluding friability)

 To evaluate the efficacy of mirikizumab compared to placebo in achieving corticosteroid-free remission without surgery among patients induced into clinical remission with mirikizumab and receiving corticosteroids at induction baseline 	
 Corticosteroid-free remission without surgery at Week 40 among induction clinical remitters, defined as: 
 Clinical remission at Week 40, and No corticosteroid use for ≥ 12 weeks prior to Week 40

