10.1. Sample Size Determination

Assuming that 90% of patients complete Study AMAN (which is expected to randomize approximately 1160 patients), Eli Lilly and Company (Lilly) anticipates approximately 1044 patients will enroll in Study AMBG. It is expected that approximately 470 of these patients will enter Study AMBG as clinical responders to mirikizumab and then will be randomized 2:1 to 200 mg mirikizumab SC (approximately 313 patients) and placebo (approximately 157 patients). Among the expected 470 mirikizumab clinical responders, approximately 180 mirikizumab clinical remitters will be randomized to 200 mg mirikizumab SC (approximately 120 patients) and placebo (approximately 60 patients). This assumes that:

- The induction study (AMAN, which has a mixed population with approximately 50% biologic-failed patients) is expected to have an overall clinical remission rate of 23% and response rate of 60% with mirikizumab.
- 75% of induction patients receive treatment with mirikizumab, based on a 3:1 randomization ratio for the induction study.
- 10% dropout rate from induction to maintenance.

The primary endpoint, clinical remission at Week 40, will be assessed on patients who achieved clinical response to mirikizumab induction treatment. Assuming mirikizumab and placebo clinical remission rates of 47% and 27%, respectively, this study based on the 470 mirikizumab induction responders is expected to have >95% power to demonstrate that mirikizumab is superior to placebo by using a chi-square test with a 2-sided significance level of 0.05. In addition, the sample size is expected to provide adequate power (>80%) to demonstrate that mirikizumab is superior to placebo for endoscopic remission, histologic remission, and corticosteroid-free remission at Week 40, among responders to mirikizumab induction treatment by using a chi-square test with a 2-sided significance level of 0.05.

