10.3.3.2. Secondary Analyses

The secondary efficacy and health outcome endpoints of the trial are presented in [Table AMBG.4.1](#) and details of the analysis methods that will be utilized are provided in Section [10.3.1](#).

The endpoints for the major secondary objectives will be analyzed using the similar CMH test used for the primary endpoint. Multiplicity adjustment for type 1 error control to the major secondary endpoints is described in Section [10.3.1.2](#).

Additional analyses of the secondary efficacy and health outcome endpoints may be considered and will be fully detailed in the SAP.

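### Does the 10% subgroup floor in Section 10.3.7.1 block the planned test of durable remission in biologic-failed patients?

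*Protocol*

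**What the plan says.** Section 10.3.7.1 opens with its scope: "Subgroup analyses will be conducted for the primary endpoint and selected major secondary endpoints". It lists the subgroup factors, biologic-failed status among them, and sets a 0.10 level for the interaction test. It then gives the floor: "If any treatment group within the subgroup is less than 10% of the total mITT population for the main cohort", in which case "only summaries of the efficacy data will be provided (that is, no inferential testing will be done". It closes by leaving the detail of the subgroup analyses to the SAP.

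Table AMBG.4.1 lists, under Other Secondary, a comparison with placebo whose aim reads "maintaining clinical remission at Week 40 (Week 52 of continuous therapy) among patients induced into clinical remission with mirikizumab, in the subgroup of patients"; the patients meant are those with biologic failure or intolerance. For secondary endpoints in that table, Section 10.3.3.2 says that "details of the analysis methods that will be utilized are provided in Section" 10.3.1, where the test for categorical endpoints is the CMH test. The Synopsis adds: "No multiplicity control approach will be used for testing of other secondary endpoints".

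The planned sizes are in Section 10.1. Of the 470 mirikizumab responders (313 mirikizumab, 157 placebo), "approximately 180 mirikizumab clinical remitters will be randomized to 200 mg mirikizumab SC (approximately 120 patients) and placebo (approximately 60 patients"). The induction study is described as a "mixed population with approximately 50% biologic-failed patients".

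**The concern.** The floor is a share of the whole main cohort, but several endpoints are assessed in only part of that cohort. Durable remission is the clearest case, because only about 60 placebo patients can contribute to it. A threshold worded as 10% would then act as 78% of the placebo patients available, and two levels of one factor could never both reach it.

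The more serious worry is a conflict over a listed objective. Biologic-failed status is a named subgroup factor, and durable remission in biologic-failed patients is a named objective. If the floor governed that objective, the comparison with placebo would be descriptive only. If the secondary-endpoint section governed, it would be tested. Were the protocol really undecided between the two, someone could choose after seeing the data whether a p-value is reported.

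**Working it through.** **1. The plan's own sizes reproduce.** Inputs from Section 10.1: 1160 randomised in induction, 90% continuing, 75% on mirikizumab, 60% response, 23% remission, 2:1 allocation.

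- Responders: 1160 × 0.90 × 0.75 × 0.60 = 469.8, stated as 470. Split 2:1, this gives 313 and 157.
- Remitters: 1160 × 0.90 × 0.75 × 0.23 = 180.1, stated as 180. Split 2:1, this gives 120 and 60.

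**2. The floor.** 0.10 × 470 = 47 per treatment group. As a share of each group:

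- all placebo patients: 47/157 = 29.9%
- all mirikizumab patients: 47/313 = 15.0%
- placebo remitters: 47/60 = 78.3%

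**3. Which section covers the objective.**

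| Item | Status in Table AMBG.4.1 | Covered by |
|---|---|---|
| Clinical remission among responders | Primary | 10.3.3.1; subgroups in 10.3.7.1 |
| Durable remission, all remitters | Major Secondary | 10.3.3.2; subgroups in 10.3.7.1 only if selected |
| Durable remission, biologic-failed remitters | Other Secondary | 10.3.3.2, hence the methods of 10.3.1 |

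The third row lies outside the stated scope of Section 10.3.7.1. Sections 10.3.3.2 and 10.3.1 and the Synopsis agree that it is tested, without multiplicity control. No sentence applies the floor to it.

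**4. Which patients are counted.** The floor compares a treatment group within a subgroup with the total main-cohort mITT population. Two counts are possible for biologic-failed status on placebo. Both assume that the 50% share in induction carries over; the protocol gives no share among responders or remitters.

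- Remitters only: 60 × 0.5 = 30, below 47. At shares of 30% and 70% the counts are 18 and 42. The floor is reached only above a share of about 78%. Two levels would need 2 × 47 = 94, more than 60.
- Main-cohort patients in the subgroup: 157 × 0.5 = 78.5, above 47. On mirikizumab, 313 × 0.5 = 156.5. The floor is reached from a share of 47/157 = 29.9% upwards.

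The second count takes numerator and denominator from the same population. The first mixes a remitter numerator with an all-responder denominator. The 78% and the 94-against-60 argument exist only under the first.

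**5. The primary endpoint.** Biologic-failed status has about 78 placebo patients per level. Induction remission status has 60 and 157 − 60 = 97. All exceed 47.

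**6. What a floor based on each endpoint's own population would do.** For remitters it would be 0.10 × 180 = 18 per group, so 36 mirikizumab against 18 placebo at 2:1. The 95% half-width for a risk difference is 1.96 × √(p₁q₁/n₁ + p₀q₀/n₀). The 47% and 27% are the protocol's primary-endpoint rates, used here for illustration.

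| n (mirikizumab, placebo) | 47% v 27% | 50% v 50% |
|---|---|---|
| 94, 47 | 16.2 points | 17.5 points |
| 36, 18 | 26.2 points | 28.3 points |

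**The case for a change.** The best argument for the concern is that the same comparison can be reached by two routes. Durable remission is itself a major secondary endpoint and biologic-failed status is a listed factor. If durable remission is selected for subgroup analysis and the count is taken among remitters, Section 10.3.7.1 would give a summary where Section 10.3.3.2 gives a test. No sentence exempts the listed objective, and the denominator of the floor is already fixed in the protocol.

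Part of this stands. The arithmetic is right, the floor does name the whole main cohort, and the protocol does not say which patients are counted for an endpoint assessed in part of it. But two conditions must hold together: that durable remission is selected, and that remitters alone are counted. The protocol states neither, and both are details that a protocol may leave to the SAP. Even if both held, a limit on what the subgroup section reports would not withdraw an analysis that another section assigns to a separately listed objective. An exemption sentence would only write down what already follows.

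It is also too broad to say that every factor would lose a level. Induction remission status is listed only for endpoints among induction responders, so it is not a factor for durable remission.

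Setting the floor against each endpoint's own population is a reasonable preference, but it has a price. It would allow tests with 18 placebo patients and half-widths of 26 to 28 points, against 16 to 18 points at 47. Precision depends on absolute counts, so holding one minimum across endpoints can be defended.

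**Conclusion.** The concern does not hold. On planned numbers the floor is 47 per treatment group, and about 30 biologic-failed placebo remitters would indeed fall below it. But the section that sets the floor does not cover that Other Secondary objective, and the sections that do cover it provide for a test. The claim that 10% works as 78% rests on an endpoint selection the protocol does not make and on a count it does not prescribe; the other available count gives about 78 placebo patients and passes.

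Following the plan as written gives no wrong result. Levels below the floor are still summarised, the floor is met for biologic-failed status and induction remission status on the primary endpoint, and the primary and multiplicity-controlled tests are untouched.

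This rests on the planned main cohort of 470 (the floor moves with the actual mITT count) and on a biologic-failed share near 50%. The SAP was not available for this check, so how it counts patients or selects endpoints is not judged here.

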10.3.8. Interim Analyses

One DMC consisting of members external to Lilly will be established for periodic monitoring of clinical trial data across all Phase 3 trials for the UC adult program. This committee will consist of a minimum of 3 members, including a physician with expertise in gastroenterology and a statistician. No member of the DMC may have contact with study sites. A statistical analysis center (SAC) will prepare and provide unblinded data to the DMC. The SAC members may be Lilly employees or from third-party organizations designated by Lilly. However, they will be external to the study team and will have no contact with sites and no privileges to influence changes to the ongoing studies. The timing and frequency of the periodic clinical trial data review by the DMC will be detailed in the DMC charter for the UC adult program.

A primary database lock is planned after all patients complete the Week 40 visit or the ETV. The analysis based on data from the primary database lock will be conducted by the sponsor or a designee and no further multiplicity adjustment will be implemented. The final database lock will occur after all patients complete the entire study, including safety follow-up.

The DMC is authorized to evaluate unblinded interim efficacy and safety analyses during the periodic safety review. The DMC will make recommendation to the Lilly Research Laboratories Senior Management Designee, who may order the immediate implementation of the DMC recommendation, or may convene an internal review committee (IRC), which is independent from the study team, to review the recommendation according to standard Lilly policy. Study sites will receive information about interim results ONLY if they need to know for the safety of their patients.

In addition to DMC, SAC, and potential IRC, a limited number of pre-identified individuals may gain access to the limited unblinded data, as specified in the unblinding plan, prior to the interim or final database lock, in order to initiate the final population PK/PD model development processes for interim or final analyses. Information that may unblind the study during the analyses will not be shared to the study sites or the blinded study team until the study has been unblinded. Unblinding details will be specified in the unblinding plan section of the SAP or a separate unblinding plan document.

11. References

Appendix 1. Abbreviations and Definitions

Term	Definition
5-ASA	5-aminosalicylic acid
6-MP	6-mercaptopurine
ADA	Anti-drug antibody
ADR	adverse drug reactions
AE	adverse event: Any untoward medical occurrence in a patient or clinical investigation patient administered a pharmaceutical product that does not necessarily have a causal relationship with this treatment. An adverse event can therefore be any unfavorable and unintended sign (including an abnormal laboratory finding), symptom, or disease temporally associated with the use of a medicinal (investigational) product, whether or not related to the medicinal (investigational) product.
AESI	adverse events of special interest
ALP	alkaline phosphatase
ALT	alanine aminotransferase
anti-HBc	anti-hepatitis B core antibody
AST	aspartate aminotransferase
AZA	azathioprine
BCG	Bacillus Calmette-Guerin
blinding	A double-blind study is one in which neither the patient nor the investigator or sponsor staff who are involved in the treatment or clinical evaluation of the patients are aware of the treatment received.
CI	confidence interval
clinical research physician	Individual responsible for the medical conduct of the study. Responsibilities of the clinical research physician may be performed by a physician, clinical research scientist, global safety physician, or other medical officer.
CMH	Cochran-Mantel-Haenszel
complaint	Any written, electronic, or oral communication that alleges deficiencies related to the identity, quality, purity, durability, reliability, safety or effectiveness, or performance of a drug or drug delivery system.
compliance	Adherence to all study-related, good clinical practice, and applicable regulatory requirements.
CRP	C-reactive protein
CSR	clinical study report

C-SSRS	Columbia-Suicide Severity Rating Scale
DALM	dysplasia-associated lesion or mass
DMC	Data Monitoring Committee
ECG	electrocardiogram
eCOA	electronic clinical outcome assessment
eCRF	electronic case report form
EIM	extraintestinal manifestations
enroll	The act of assigning a patient to a treatment. Patients who are enrolled in the study are those who have been assigned to a treatment.
enter	Patients entered into a study are those who sign the informed consent form directly or through their legally acceptable representatives.
EQ-5D 5L	European Quality of Life 5-Dimension 5 Level
ERB	ethical review board
ES	endoscopic subscore(s)
ETV	early termination visit
EUDRA	European Union Drug Regulatory Authorities
FSH	follicle-stimulating hormone
FWER	family-wise type I error rate
GEMINI 1	Phase 3, Randomized, Placebo-Controlled, Blinded, Multicenter Study of the Induction and Maintenance of Clinical Response and Remission by Vedolizumab (MLN0002) in Patients with Moderate to Severe Ulcerative Colitis (GEMINI 1)
GCP	Good Clinical Practice
GMP	Good Manufacturing Practices
HBsAg	hepatitis B surface antigen
HBV	hepatitis B virus
HCV	hepatitis C virus
IB	Investigator's Brochure
IBDQ	Inflammatory Bowel Disease Questionnaire
ICF	informed consent form

ICH	International Council for Harmonisation
IgG4	immunoglobulin G4
IL	interleukin
IRC	internal review committee
IV	intravenous
informed consent	A process by which a patient voluntarily confirms his or her willingness to participate in a particular study after having been informed of all aspects of the study that are relevant to the patient decision to participate. Informed consent is documented by means of a written, signed, and dated informed consent form.
interim analysis	An analysis of clinical study data, separated into treatment groups, that is conducted before the final reporting database is created/locked.
investigational product	A pharmaceutical form of an active ingredient or placebo being tested or used as a reference in a clinical trial, including products already on the market when used or assembled (formulated or packaged) in a way different from the authorized form, or marketed products used for an unauthorized indication, or marketed products used to gain further information about the authorized form.
IWRS	interactive web-response system
LOR	Loss of Response
LS	least squares
LTBI	latent tuberculosis infection
mITT	All randomized/enrolled patients who received at least 1 dose of study treatment, do not receive the correct treatment, or otherwise do not follow the protocol. Patients will be analyzed according to the treatment to which they were assigned
MMRM	mixed-effects model of repeated measures
MMS	modified Mayo Score
MOS	margin of safety
NOAEL	no-observed-adverse-effect level
NRI	nonresponder imputation
NRS	numeric rating scale
PASI	Psoriasis Area and Severity Index
PD	pharmacodynamic(s)

PGA	Physician's Global Assessment
PGRC	Patient's Global Rating of Change
PGRS	Patient's Global Rating of Severity
PK	pharmacokinetic(s)
PRO	patient-reported outcomes
Q4W	every 4 weeks
QIDS-SR16	Quick Inventory of Depressive Symptomatology —Self-Report (16 Items)
RB	rectal bleeding
SAE	serious adverse event
SAC	statistical analysis center
SAP	statistical analysis plan
SC	subcutaneous
SF	stool frequency
SF-36	Medical Outcomes Study 36-Item Short Form Health Survey
screen	The act of determining if an individual meets minimum requirements to become part of a pool of potential candidates for participation in a clinical study.
SUSAR	suspected unexpected serious adverse reaction
TB	tuberculosis
TBL	total bilirubin level
TE-ADA	treatment-emergent antidrug antibody
TEAE	treatment-emergent adverse event
UC	ulcerative colitis
UCEIS	Ulcerative Colitis Endoscopic Index of Severity
ULN	upper limit of normal
UV	unscheduled visit
WPAI:UC	Work Productivity and Activity Impairment Questionnaire Ulcerative Colitis

